9.2.2 Secondary Endpoints

1. Adverse Events

The percentage of subjects experiencing one or more adverse events will be calculated. The frequency of adverse events will be reported as a proportion of the total number of infusions with Alphanate®. Causality [the proportions of adverse events judged to be definitely, probably, possibly, probably not and definitely not related to treatments with Alphanate®] and severity will be reported as percentages of the total number of adverse events occurring during the course of the clinical trial.

2. Assessment of Biochemical Tests on Serum

Descriptive statistics will be presented, with a focus on parameters which when elevated may indicate alterations in hepatic or renal function.

3. Viral Safety

Viral safety will be determined by a lack of seroconversion to reactivity against the specific blood-borne viruses for which subjects will have been tested and found to be nonreactive at the time of enrollment.

4. Consumption Analysis

Descriptive statistics will be employed to evaluate the use of Alphanate® by subjects, both for self-administration and for treatment by the investigator at the clinical site or other places of treatment.

5. Hemostasis

Descriptive statistics will be employed to evaluate the physicians' qualitative assessments of the ability of Alphanate® to control bleeding episodes when administered at the clinical site.

Contains Confidential and Proprietary Information of Grifols Inc.

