5.1 Inclusion Criteria

1. The subject must be male, at least six years of age and not more than 65 years of age.
2. The subject must have signed and dated an Informed Consent Form and Patient Authorization for Release of Information approved by the appropriate Institutional Review Board (IRB) prior to screening and enrollment. If the subject is a minor (*i.e.*, less than 18 years of age) both he and his parent or legal guardian must sign and date the informed consent.
3. The subject must have been diagnosed with severe hemophilia A and must have levels of Factor VIII less than 0.01 IU/mL.
4. The subject must have received treatment with cryoprecipitate, Factor VIII concentrates, and/or whole blood, for at least 150 cumulative exposure days (CEDs) prior to enrollment.
5. The subject must not have received treatment with cryoprecipitate, Factor VIII concentrate, or any other blood product, for at least 72 hours prior to screening.
6. The subject must never have been diagnosed with inhibitors to Factor VIII at any detectable titer.

Contains Confidential and Proprietary Information of Grifols Inc.

7. The subject must never have been diagnosed with nonspecific inhibitors of coagulation.
8. The subject must test negative for the presence of Factor VIII inhibitors at screening and enrollment.
9. The subject must have CD4 counts greater than or equal to 400 cells/ μ L.
10. The subject must have been vaccinated against hepatitis A and hepatitis B, or have evidence of antibodies against hepatitis A and hepatitis B. However, a subject who has no prior immunity against hepatitis A will be offered a course of vaccination for hepatitis A.
11. The subject must have a Kamofsky Performance Score of at least 50 (Appendix 1).

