8.2 Secondary Endpoints

All subjects will be considered to be evaluable for the secondary endpoints.

1. The frequency, nature, causality and severity of adverse events.
2. The occurrence of variations in biochemical parameters which would indicate renal or hepatic impairment.
3. Evidence for seroconversion to HIV-1/HIV-2, HAV, HBV, HCV and parvovirus B19 for subjects who are seronegative for these viruses upon enrollment.
4. The amount of product used per year as part of at-home prophylaxis and therapy for bleeding episodes.
5. A physician's qualitative assessment of hemostasis (evaluated as "None," "Moderate," "Good," or "Excellent") in response to therapy with Alphanate[®] received by the subject in a hospital or at another location under the physician's direct supervision.

With this section, the design of this clinical trial satisfies the recommendations of the CPMP for trials in previously-treated patients of concentrates with marketing authorization in which a manufacturing process has been added.

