9 STATISTICAL PLAN

9.1 Sample Size

The sample size of 50 to 80 evaluable patients followed for at least two years for renal or hepatic function and evidence of seroconversion to HIV-1/HIV-2, HAV, HBV, HCV and parvovirus B19 is in accordance with the recommendations of the CPMP regarding post-authorization surveillance of previously-treated patients infused with a coagulation factor concentrate:

- for which a marketing authorization has already been granted and
- in the production of which a manufacturing process has been added.

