9.2 Secondary Analyses

There are both efficacy and safety endpoints. All secondary safety analyses will be conducted on the Safety Population.

Secondary efficacy analyses will be summarized with categorical descriptive statistics for the following:

- The amount of product used per year as part of at-home prophylaxis and therapy for bleeding episodes, and
- A physician's qualitative assessment of hemostasis (evaluated as "None", "Moderate", "Good", or "Excellent" in response to therapy with Alphanate® received by the subject in a hospital or another location under the physician's direct supervision).

Secondary safety analyses will be summarized with categorical descriptive statistics for the following:

- The frequency, nature, causality and severity of adverse events,
- The occurrence of changes in biochemical parameters which would indicate renal or hepatic impairment,
- The incidence of seroconversion to human immunodeficiency virus type 1 and 2 (HIV-1/HIV-2), hepatitis A virus (HAV), hepatitis B virus (HBV), hepatitis C virus (HCV) or parvovirus B19 in subjects seronegative for these viruses at the time of enrollment,

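### Viral safety is concluded from zero seroconversions whatever the number at risk, and no upper limit on the rate is planned for any virus

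*Protocol*

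**What the plan says.** Protocol 9.2.2, item 3 (Viral Safety) reads "Viral safety will be determined by a lack of seroconversion to reactivity against the specific blood-borne viruses" and limits this to viruses "for which subjects will have been tested and found to be nonreactive at the time of enrollment". It is the only item in that section that states a conclusion; the others promise percentages or descriptive statistics.

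Protocol 9.1 gives the size of the evidence as "The sample size of 50 to 80 evaluable patients followed for at least two years for renal or hepatic function and evidence of seroconversion" to the listed viruses, justified by agreement with CPMP recommendations and not by a calculation. Protocol 8.2 adds "All subjects will be considered to be evaluable for the secondary endpoints".

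Two sets of entry criteria affect who is at risk. Inclusion criterion 10 says "The subject must have been vaccinated against hepatitis A and hepatitis B, or have evidence of antibodies against hepatitis A and hepatitis B", and adds that "a subject who has no prior immunity against hepatitis A will be offered a course of vaccination for hepatitis A". Exclusion criterion 5 removes HIV-positive subjects.

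The SAP defines the endpoint as the incidence of seroconversion among subjects seronegative at enrollment (section 2.3.2). On analysis it says "Secondary safety analyses will be summarized with categorical descriptive statistics for the following" (section 9.2), and section 6.6 defines such statistics for categorical data as frequencies and percentages. Tables 12.11 and 12.14 are listed as summaries of viral serology and viral infection. No interval is mentioned.

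**The concern.** Zero events are evidence of safety only to the extent that the number at risk makes events likely if the risk is real. The protocol sentence turns zero events into a conclusion without using that number, and the SAP does not supply the missing limit. A 0% in the table supports the same words whether it rests on a few subjects or on the full cohort.

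The relevant denominator is the subset nonreactive for that virus at enrollment, and not the 50 to 80 in section 9.1. Because all subjects count as evaluable for secondary endpoints, nothing requires a subject to have any follow-up serology before he counts as not having seroconverted.

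What is at stake is the strength of a secondary safety statement. Protocol section 6 itself says that virus reduction and testing do not remove the risk of transmission entirely, so readers will want to know what rate the trial can rule out.

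**Working it through.** **The plan's own figure.** There is none to reproduce. The documents give no rate, limit, power or number at risk for seroconversion.

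**Inputs.**
- Rule: zero seroconversions (Protocol 9.2.2, item 3).
- Ceiling on the number at risk: 50 to 80 (Protocol 9.1).
- Number at risk per virus: not stated. I use 50 and 80 as the ceiling, and 5, 10 and 20 as assumed smaller sets.
- Confidence level: 95%. Protocol 9.2.1 uses a one-sided interval for the primary endpoint and SAP 6.5 sets two-sided testing as the default, so both limits are shown.
- True risks of 5% and 10%: assumptions, for illustration only.

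**Formulas.** For zero events in n subjects, the exact (Clopper-Pearson) upper limit is 1 − 0.05^(1/n) one-sided and 1 − 0.025^(1/n) two-sided. If the true risk is p, the chance of zero events is (1 − p)^n.

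| At risk, n | One-sided 95% limit | Two-sided 95% limit | Chance of zero events at 5% risk | Chance of zero events at 10% risk |
|---|---|---|---|---|
| 5 | 45.1% | 52.2% | 77% | 59% |
| 10 | 25.9% | 30.8% | 60% | 35% |
| 20 | 13.9% | 16.8% | 36% | 12% |
| 50 | 5.8% | 7.1% | 7.7% | 0.5% |
| 80 | 3.7% | 4.5% | 1.7% | below 0.1% |

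Worked examples: for n = 50, 1 − 0.05^(1/50) = 0.058; for n = 10 at 10% risk, 0.9^10 = 0.35.

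**Number needed.** To exclude a 5% risk with zero events, n must be at least ln(0.05)/ln(0.95) = 58.4, so 59 subjects one-sided. The two-sided figure is ln(0.025)/ln(0.95) = 71.9, so 72. Fifty subjects do not reach this even if all are at risk; eighty do.

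**What the documents allow one to say about n, by virus.**
- HIV: positive subjects are excluded, so n is close to the whole cohort.
- Hepatitis A: criterion 10 requires vaccination or antibody and offers vaccine to the non-immune, so n may be reduced.
- Hepatitis B: the same criterion applies, so n may be reduced. Three markers are tested (HBsAg, HBcAb, HBsAb), and neither document says which of them defines being at risk.
- Hepatitis C and parvovirus B19: no entry criterion on serostatus and no baseline count, so n is unknown.

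**The case against.** The strongest reply is that this is one sentence about a secondary endpoint, with no hypothesis, margin or consequence attached. The SAP calls its analysis mainly descriptive and names the endpoint as an incidence among seronegative subjects. A percentage of that kind implies a denominator, so a reader could probably tell zero of 5 from zero of 50 and work out the limit. That stands, and it limits the matter to the strength of the stated conclusion. It does not remove the rule: the protocol still says how viral safety is determined, and that sentence ignores the denominator.

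Three stronger readings are tempting, and the documents do not support them.
- A reader might infer that only a handful of subjects will be at risk for hepatitis C or parvovirus B19, given at least 150 earlier exposure days. Neither document gives a seronegative count or a prevalence for either virus.
- A reader might infer that the rule is likely to declare safety when transmission is real. At an assumed 10% risk, zero events are more likely than not only for very small sets: 59% with 5 at risk, but 35% with 10, 12% with 20 and 0.5% with 50. The 10% has no basis in the documents, which describe donor screening and two viral reduction steps.
- A reader might take section 9.1 to claim 50 to 80 subjects at risk for each virus. It says only that the total accords with CPMP recommendations.

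It is also fair to object that for hepatitis A the error may run the other way. Subjects vaccinated on study can become antibody-positive and would count as seroconversions under the bare rule. That stands too, and the remedy has to deal with it.

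**Conclusion.** The concern holds as a limit on what may be concluded. Viral safety is to be concluded from zero seroconversions regardless of the number at risk, and the SAP adds no upper limit. In the best case, with 50 or 80 subjects at risk, zero events leave seroconversion risks up to 5.8% or 3.7% compatible with the data (one-sided 95%). If the set at risk for some virus were 20, 10 or 5, the limit would be 14%, 26% or 45%. Those smaller sets are assumptions. Criterion 10 makes reduced numbers possible for hepatitis A and perhaps hepatitis B, the documents are silent for hepatitis C and parvovirus B19, and small numbers are not an issue for HIV.

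The calculation treats each subject as one independent observation with complete follow-up. It does not show that the product transmits virus or that a false assurance is likely. It shows that the rule can state more than the data support. The change is worth making before analysis; it does not affect the primary endpoint or the sample size.

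**What to change.** Replace the sentence in Protocol 9.2.2, item 3, and add the same to SAP 9.2 and Table 12.14:

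- For each virus separately, report seroconversions over the number of subjects nonreactive at baseline with at least one follow-up serology result, with the exact one-sided 95% upper limit.
- Word the conclusion as a rate excluded: *rates above X% are excluded*.
- Identify antibody attributable to hepatitis A or B vaccination and do not count it as seroconversion from the product. For example, show subjects vaccinated on study separately, and judge hepatitis B on HBsAg and HBcAb. Without this step the upper limit would treat vaccine responses as transmissions.

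Section 9.1 can stay as the total enrolled. The number at risk per virus cannot be known before enrollment, so it should be reported at analysis as the basis of the viral-safety statement.

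The cost is a few sentences and an extra column or two in a planned table, with no new samples or visits. Vaccination data are already to be listed (Listing 10.8). The downside is a less favourable-looking statement for any virus with few subjects at risk.

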10 ADVERSE EVENTS

Any adverse events observed by the investigator or study staff or reported by the subject and which occur during the study will be recorded on the appropriate case report form. These events will be reported regardless of the perceived relation of the event to study treatment.

10.1 Adverse Event Monitoring

At each visit of the subject to his treatment center an assessment will be performed of any adverse events occurring since the previous visit. Any adverse event, which is observed by the investigator or study staff or reported by the subject and which occurs during the study, will be reported on the appropriate CRF. Any substantive or unexpected new abnormality will be recorded and monitored until the abnormal finding returns to normal for that subject.

Each new event that appears to be independent of any prior event will be reported separately. The description of the event will include:

- its nature,
- the date of onset,
- the duration and severity of each sign or symptom,
- the investigator's opinion regarding the likelihood of causal relationship to the study drug,
- the course of action taken and
- the resolution of the event.

10.2 Serious Adverse Events

Any serious adverse event, including death, that occurs while the subject is receiving an investigational drug, irrespective of the investigator's opinion regarding drug relationship, will be reported by telephone **within 24 hours of its occurrence** to the Grifols' Personnel assigned to the study, [REDACTED], who can be contacted during working hours (8:00 a.m. to 5:00 p.m. Pacific Time) at [REDACTED] or [REDACTED] during non-working hours.

A **serious** adverse event is defined by FDA regulations in the Code of Federal Regulations (21 CFR 312.32) as any adverse event that suggests a significant hazard, contraindication, side effect or precaution. With respect to human clinical events, a serious event includes any event that results in the following outcomes: Death, a life-threatening adverse drug event, inpatient hospitalization or prolongation of existing hospitalization, a persistent or significant disability/incapacity, or a congenital anomaly/birth defect. Important medical events that may not result in death, be life-threatening, or require

Contains Confidential and Proprietary Information of Grifols Inc.

hospitalization may be considered serious adverse drug events when, based upon appropriate medical judgment, they may jeopardize the patient or subject and may require medical or surgical intervention to prevent one of the outcomes listed in the definition.

If a serious adverse event occurs, based on the investigator's judgment, appropriate therapy should be administered. Subjects will then be monitored closely as appropriate.

Oral reports of serious adverse events must be confirmed in writing within five (5) calendar days of the occurrence to Grifols Inc. and to the Institutional Review Board within their reporting guidelines.

10.3 Grading Scale

An adverse event may occur during or following the administration of the investigational compound or control agent. Each event will be graded according to severity using the following criteria as appropriate:

- **Mild:** the event was noted but the administration of the compound was not interrupted; the event resolved spontaneously or no treatment was required beyond administration of nonprescription analgesics.
- **Moderate:** the administration of the compound was not necessarily interrupted; the event required momentary treatment with prescription drugs and produced no sequelae.
- **Severe:** the event caused interruption of the administration of the compound, produced sequelae and required prolonged treatment. Infusion of the compound will not be resumed until all symptoms are resolved.

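### The only adverse-event severity scale (Protocol 10.3) leaves some events without a grade, so the severity summaries may rest on inconsistent or missing grades

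*Protocol*

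**What the plan says.** Protocol 10.3 instructs: "Each event will be graded according to severity using the following criteria as appropriate". It then defines three grades.

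- **Mild:** administration was not interrupted, and "the event resolved spontaneously or no treatment was required beyond administration of nonprescription analgesics".
- **Moderate:** interruption is possible but not required, and "the event required momentary treatment with prescription drugs and produced no sequelae".
- **Severe:** this grade joins three conditions, all of which must be met: "the event caused interruption of the administration of the compound, produced sequelae and required prolonged treatment". A further sentence forbids restarting the infusion while any symptom persists.

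There is no residual grade and no rule for an event that meets only some of the Severe conditions.

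The scale covers every event recorded. Protocol section 10 states: "These events will be reported regardless of the perceived relation of the event to study treatment". Follow-up lasts at least two years (Protocol section 4), and Alphanate may be self-administered at home (7.7, 7.9.1).

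Severity is part of the first secondary endpoint in Protocol 8.2: "The frequency, nature, causality and severity of adverse events". Under Protocol 9.2.2, "severity will be reported as percentages of the total number of adverse events occurring during the course of the clinical trial". SAP 9.2.1 takes the highest severity when an event recurs in a subject, and SAP Table 12.3 summarises events by greatest severity. The SAP does not define severity.

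**The concern.** The scale is built around stopping an infusion, but it is applied to all illness over two years or more. Interruption is an action taken, not a measure of intensity. A subject who depends on Alphanate as his only factor VIII product may have no reason to stop it for an unrelated illness.

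Every event has to be graded, yet some fit no definition. A site must then either leave the grade blank or pick one by its own rule, and two sites could grade the same event differently. SAP 7.1 rules out imputation, and no rule covers events without a grade. At stake is whether the severity part of secondary endpoint 1 can be interpreted.

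**Working it through.** There is no stated figure to reproduce. The check is whether the three definitions cover all events.

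**Inputs (Protocol 10.3).** Each definition is taken literally:

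- Mild = no interruption AND (spontaneous resolution OR nothing beyond nonprescription analgesics).
- Moderate = momentary prescription treatment AND no sequelae, with or without interruption.
- Severe = interruption AND sequelae AND prolonged treatment.

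**Grid.** Interruption (2 levels) × treatment (5) × sequelae (2) = 20 combinations. The five treatment levels are this review's own grouping of the protocol's wording.

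| Treatment | Not interrupted, no sequelae | Not interrupted, sequelae | Interrupted, no sequelae | Interrupted, sequelae |
|---|---|---|---|---|
| None / spontaneous resolution | Mild | Mild | none | none |
| Nonprescription analgesic, short | Mild | Mild | none | none |
| Nonprescription analgesic, prolonged | Mild | Mild | none | Severe |
| Prescription, momentary | Moderate | none | Moderate | none |
| Prescription or other, prolonged | none | none | none | Severe |

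**Count.** Mild 6, Moderate 2, Severe 2, no grade 10; 6 + 2 + 2 + 10 = 20. These are combinations of wording, not frequencies of events.

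**Three cells in words.**

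- *Infection treated with prescription drugs for weeks, Alphanate continued, full recovery.* It is not Mild (treatment went beyond analgesics), not Moderate (treatment was not momentary) and not Severe (no interruption, no sequelae).
- *Untreated event that leaves sequelae, no interruption.* It is Mild, because Mild has no condition on sequelae.
- *Reaction that stops an infusion and resolves without treatment.* It is not Mild (interrupted), not Moderate (no prescription treatment) and not Severe (no sequelae, no prolonged treatment).

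**Limit of the gap.** Prolonged use of nonprescription analgesics alone, without interruption, is Mild. The gap for prolonged treatment therefore begins beyond those drugs.

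**Do lenient readings close it?**

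- *Waive interruption for events outside an infusion.* The infection above still has no grade, because Severe also needs sequelae.
- *Read momentary as any limited prescription course.* The infection becomes Moderate, but the same event with sequelae and no interruption has no grade.
- *Do both.* Short prescription treatment with sequelae still fits neither Moderate nor Severe, and the self-resolving reaction that stopped an infusion is still ungraded.

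**The case against.** The strongest reply is that the scale was never meant to be read as a logical test. The grading instruction leaves room for judgment, and momentary has no stated duration, so a site could sensibly grade a cured infection as Moderate. The CRFs are not among the documents. If the form forces one of three grades, nothing will be missing. The facts behind each grade are also collected: Protocol 10.1 asks for the duration of signs and symptoms, the action taken and the resolution; 7.13 records every drug with its duration and indication; and SAP Listing 12.16 shows all adverse events. The study has one arm, its analysis is primarily descriptive (SAP 6.4), and no test or threshold uses severity.

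Much of this stands, and it limits the consequence. It does not remove the gap. Latitude without a criterion lets sites differ, and a forced choice would turn missing grades into inconsistent ones. The listings allow a reader to find long-treated events, but the severity tables would still mix conventions.

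A reader might go further and infer that the Severe percentage is biased downward. The documents do not support that. It would require the ungraded events to be truly severe, and the infection example could well be Moderate on an intensity scale. Nor do 10 empty cells out of 20 mean that half of all events lack a grade.

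**Conclusion.** The concern holds as a minor point. Protocol 10.3 is not exhaustive, and its open terms leave sites to settle the grade by their own convention. The severity percentages in Protocol 9.2.2 and SAP Table 12.3 may therefore rest on inconsistent or missing grades. Inconsistency between sites is inferred from the wording; it is not demonstrated. No direction or size can be given, since the documents contain no event counts and the CRFs are not visible.

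The effect is confined to descriptive summaries of mainly non-serious events. A reader might infer that the wider safety assessment is compromised, but the documents do not support this:

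- Serious events are defined without the grade (Protocol 10.2) and have their own table and listing (SAP 12.5, 12.17).
- Deaths are reported (Protocol section 11) and listed (SAP 12.18) separately.
- Discontinuation for a severe or serious event (Protocol 7.14) also requires a medical judgment that the event prevents completion.
- The primary endpoint uses central-laboratory inhibitor results (Protocol 7.8), not severity grades.

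**What to change.** Replace 10.3 with intensity grades that cover every event:

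- Mild: the subject's usual activity is not affected.
- Moderate: the event interferes with it.
- Severe: the event prevents it.

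The yardstick should be that subject's own usual activity, because a Karnofsky score of 50 is eligible (Protocol 5.1). For laboratory-only events, use the investigator's judgment of clinical significance. Record interruption, treatment and sequelae as separate items. Limit the sentence on resuming infusion to infusion-related reactions.

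For events already graded on the present scale:

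- show in Table 12.3 which scale was used;
- add a not-graded row if any grades are missing;
- list events that were serious or needed prolonged treatment but were not graded Severe. The event descriptions (10.1) and medication durations (7.13) should supply this without new data.

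The cost is a short protocol amendment, a small SAP change with one listing, and possibly one CRF item (administration interrupted, yes or no). The main drawback is two scales in one table if the change is made mid-study. No extra visits or procedures are needed.
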